Randomized studies in drug-resistant epilepsy typically involve addition of new anti-epileptic drugs. However, in clinical practice, if the patient is already taking multiple drugs, then substitution of one of the current medications commonly occurs, despite little evidence supporting this approach.²² The choice of the substitution drug depends on the mechanism of action, the pharmacokinetic profile, drug-drug interaction, and the risk of seizure exacerbation as well as patients-related factors. The new combination is intended to maximize efficacy and minimize toxicity. However, the availability and cost-effectiveness should also be

taken into consideration since the patient would not reach the goal of ideal combination of drugs if they could not afford it nor even get the medication. ²³⁻²⁶ Another considerable case is one of drug resistance patterns in which at the first-time patients may not responsive to treatment yet they change into a state that is responsive to the medication. ²⁷ The choice of substitution therapy may originate from firs-line AEDs since evidences have shown they have equal efficacy to those of second-line ones. However, there is still lack of evidence whether the drug resistance pattern occur if the substitution drug is originated from first-line AED even more if it has ever been given prior to the current drug combination. ²⁷ The study aims to analyzed the efficacy and safety of first-line AEDs as substitution therapy in drug-resistant epilepsy children.

Primary Objective

The primary outcome of the research is to analyze the proportion of responders, who are defined as subjects who get 50% of seizure reduction.

Secondary Objectives

There are some secondary objectives of the study. The first one is to analyze the differences of improvement of quality of life, EEG feature and time to achieve seizure reduction, between the intervention and the control group. Besides, the research will describe the clinical characteristics, adverse effects of the drugs and laboratory features related to the adverse effects, among children with drug-resistant epilepsy. Furthermore, it will explain factors influencing the reduction of seizure frequency

Study Design

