including seizure frequency, seizure type, seizure onset, medication history, family history of seizure, and also developmental stages, will be recorded from electronic medical record. Besides, the CT-scan or MRI are also collected from the same source. After that, their quality of life will be assessed by QOLCE-55 validated questionnaire through self-guided report. Furthermore, the laboratory investigation and EEG will be performed.

The next phase is intervention phase, started from initial step and ended by the maintenance of new combination therapy, which takes with overall 12 weeks. Initially, the substitution drugs with each initial dose are consumed. The drugs consist of valproic acid for the generalized and carbamazepine for focal epilepsies. On the other hand, the control group will take lamotrigine or clobazam for generalized and oxcarbazepine for focal ones. The phase continuous to titration dose, in which, the dose is raised gradually until it causes 50% of seizure reduction, and the next step is maintained the dose for about 2 weeks.

The following is tapering-off and after that stopping the substituted drug, levetiracetam or topiramate, which is determined by considering individual condition. Yet, if the seizures increase more than one and a half time of the previous frequency during the phases, the intervention will be ended immediately. On the contrary, if the condition is better, then the children go to the maintenance of new combination, that is the substitution drug and the old drugs in which the seizures do not go up or even better keep going down. The children who complete all of the phases are categorized as responder. In case if the intervention is ended, the subjects will be given the former combination therapy with adjusted doses in order to decrease the seizures until reaching the pre-intervention condition. The subjects are categorized as non-responder, and will be dropped-out. The other criteria of drop-out are resignation, non-compliance of study procedure, and death in term of other causal not related to the study. While in term of lost to follow-up, is intended for those who do not attend the study without any possible reasons.

[figure not shown]

Figure 2. flow-chart of the study

Maintenance the dose of the new combination therapy that consist of the new drug and

Maintenance

old drug after stopping the substituted drug

Inclusion criteria

- 1. Children age at 1 18 years old

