- 2. Children diagnosed as drug-resistant epilepsy by pediatric neurologists, diagnosis was based on the ILAE 2017 criteria
- 3. Children will have got at least 3 months of combination therapy that consists of levetiracetam of topiramate with optimal of therapeutic dosages

Exclusion criteria

- 1. Non-convulsive epilepsy
- 2. Suffered from status epilepticus in the prior 3 months before the study begins
- 3. Past medical history of idiosyncrasies or severe adverse drug reactions caused by the substitution therapy that will be given

Instrument of the study

QOLCE-55 questionnaire

Once the children are enrolled, quality of life will be assessed by using validated QOLCE-55 questionnaire. It is parent-reported and self-administered questionnaire which assess quality of life children with epilepsy age 4-18 years of age. The researcher will give a detail explanation about filling the questionnaire. It has 55 questions including cognitive (22 items), emotional (17 items), social (7 items) and also physical (9 items) function. Items are rated on a five-point Likert scale, 0 = very often, 1 = fairly often, 2 = sometime, 3 = almost never, 5 = never. The composite score is the unweighted average of the four subscales, ranging from 1-100, higher score indicates better quality of life.²⁸

Diary Card

The other important thing to evaluate is subjects' adherence, seizure frequencies, and adverse drug reaction by self-reported diary card which is filled by the parents each day during the intervention phase. Besides, drug consumption compliance is also assessed by counting the tablets or powder packages during routine visits of the study.

Electronic Medical Record

Electronic Medical Record is used to collect secondary data that include demographic data, clinical characteristic, and imaging such as brain-CT or brain-MRI.

Laboratory Examination

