- current anticonvulsant(s) with doses and formulation and its side effect (if presents)
- other medications and its side effect (if presents)

- first recognized seizure date
- prior EEG and laboratory which has been performed at the baseline phase
- physical examination

Follow-up data

Follow-up data will be collected during regularly scheduled clinic visits (per 2 weeks). This information will be obtained from the participants' diary card. Important information to be collected at follow-up will include:

- physical examination
- adverse drug reaction of the substitution therapy that happen
- seizure's frequency
- type of seizure
- complaint

Outcome evaluation

- a. The difference in responders was the difference in the percentage of responders in the group that used first line OAE again as substitution therapy and those that used standard therapy. Responders are subjects who experience a decrease frequency of seizure more than or equal to 50% of the initial seizure. Frequency of seizure is the number of seizures that occur within 1 month. In previous studies, it was said that the frequency of seizures was said to have decreased significantly or was said to respond if the seizures were reduced by 50% or more from the initial seizure. ^{19, 29} Based on this, researchers will categorize the frequency of seizures into:
 - Responder: there is a decrease in the frequency of seizures by 50% or more than before
 - Non-responder: namely the frequency of seizures remains or decreases but not up to 50% of the initial seizure frequency or the frequency is more than before

Furthermore, the proportion in the form of the percentage of respondents in the two groups is calculated and differentiated, therefore it is classified into two groups:

- Different : when a significant difference is shown in difference of proportion test of the 2 unpaired groups.
- Not different: when there is no significant difference is shown in difference of proportion test of the 2 unpaired groups.

- b. Differences in quality of life: quality of life assessment using QOLCE-55 instrument. The average of each function (cognitive, emotional, social and physical functions) and the average of the total functions are assessed. This variable is categorized into:
 - Different, if there is a difference in the average quality of life
 - Not different, if there is no difference in the average quality of life
- c. Differences in electroencephalography appearance

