P1 proportion of reduced seizure on the new drug (the proportion of reduced seizure on the standard drug in addition to the minimal difference that is considered significant)= 0.7 + 0.25 = 0.95

Q1
$$1 - P1 = 1 - 0.95 = 0.5$$

P
$$(P1 + P2) / 2 = (0.95 + 0.7) / 2 = 0.825$$

Q
$$1-P = 1-0.825 = 0.175$$

In this study, it was found that the proportion of seizure reduction on standard drugs was 70%.³⁰ Therefore the equation:

$$n1 = n2 = \left(\frac{1,96\sqrt{2(0,825)(0,175)} + 0,84\sqrt{(0,95)(0,5) + (0,7)(0,3)}}{0,25}\right)^2 = 49,56 = 50$$

$$n\ 2\ groups=100$$

Based on the formula above, 100 research subjects are required. An additional of 10% from the total number of subjects are needed as there is a possibility of those dropping out, therefore a total of 110 subjects are needed in this study.

Statistical Analysis

- 1. Analysis of differences in the proportion of responders (primary outcome), differences in EEG appearance (secondary outcome) in pediatric epilepsy patients who are resistant to the combination of second line OAE between those who reused first line OAE as substitution therapy and those who used standard therapy. Data type is categorical. Data is analyzed the Chi-square statistical test, if it does not meet the requirements then an alternative test is performed, known as Fisher's multiple test. The significance level (α) is 5% and the research confidence level is 80%. If p value ≤ α is obtained, this means H0 is rejected, which means that there is a difference seen in seizure frequency between reusing first line OAE as substitution therapy and standard therapy.
- 2. Analysis of differences in the mean quality of life with an unpaired T test if the data distribution is normal or Mann-Whitney if data distribution is not normal
- 3. To assess drug effectiveness, the analysis used was the difference in actual failure between those using first line OAE as substitution therapy and those using standard therapy (primary outcome). Formula:

$$ARR = CER - EER$$

CER: the incidence of increased seizure frequency in the standard therapy group ERR: the incidence of increased seizure frequency in the group in substitution therapy with 1st line OAE The increase in seizure frequency in this study shows therapy

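### Study procedure calls every child who completes all phases a responder, a rule with no seizure threshold that can contradict the 50% monthly reduction defining the primary outcome

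*Combined protocol and SAP*

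**What the plan says.** The protocol contains two rules for the responder label.

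- **Reduction rule.** The Primary Objective is to analyse "the proportion of responders, who are defined as subjects who get 50% of seizure reduction". Outcome evaluation (a) repeats this as a fall of at least 50% from the initial level and fixes the unit: "Frequency of seizure is the number of seizures that occur within 1 month". It counts as a non-responder a child for whom "the frequency of seizures remains or decreases but not up to 50% of the initial seizure frequency". Statistical Analysis item 1 compares the responder proportion between arms as the primary outcome.
- **Completion rule.** Study procedure says "The children who complete all of the phases are categorized as responder". Children whose intervention is ended are classed as non-responders and dropped out.

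The steps leading to completion are also in Study procedure. The dose is raised until seizures have fallen by 50% and is held for about 2 weeks. Levetiracetam or topiramate is then tapered and stopped. The stopping trigger is: "if the seizures increase more than one and a half time of the previous frequency during the phases, the intervention will be ended immediately". A child whose condition has improved moves to maintenance on the new combination, described as one "in which the seizures do not go up or even better keep going down". Neither the improvement nor the absence of a rise is given a reference level, and no action is stated for a rise smaller than the trigger.

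**The concern.** A primary outcome needs one definition. Here the same diary can give a child opposite labels depending on the section that the analyst follows, and the plan sets no order of precedence.

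The timing makes the conflict more than verbal. The 50% fall that Study procedure relies on is seen while the child takes both the new drug and the drug to be replaced. The trial asks about substitution, so what matters is seizure control after the old drug is withdrawn. Completion does not by itself show that the 50% fall was kept.

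If the completion rule were used, some children who fall short of 50% would count as responders. If this happened to a similar degree in both arms, it would dilute the contrast. In an open-label trial, an unsettled primary label also leaves room to choose between definitions after the results are known.

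**Working it through.** **Step 1: what a completer's frequency can be.** Inputs from Study procedure: titration target 0.50 of baseline; trigger strictly above 1.5 times the previous frequency. The baseline of 12 a month is an example, since the documents give no baseline rate.

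- After titration: 12 × 0.50 = 6 a month.
- Trigger if the previous frequency is the post-titration level: 1.5 × 6 = 9. A child at 9 is not above it and is not stopped.
- Reduction from baseline at 9: 1 − 9/12 = 25%.

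Whether this child completes depends on what improvement is measured against:

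| Reading of the entry condition | Highest final level | Do the rules agree? |
|---|---|---|
| Better than baseline | 0.50 × 1.5 = 0.75 of baseline | No: responder by completion, non-responder by reduction |
| Better than the post-titration level, and not rising from it | 0.50 of baseline | Yes |

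The clash can also run the other way. A child who falls to 0.20 of baseline and then rises to 0.31 has risen by a factor of 0.31/0.20 = 1.55. That is above 1.5, so the child is stopped and labelled a non-responder while still 69% below baseline.

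**Step 2: the plan's own sample size.** Inputs from Sample size: z values 1.96 and 0.84, P1 = 0.95, P2 = 0.70. With Q1 as printed (0.5), the plan's formula gives 48.91, so 49; the plan prints 49.56 and uses 50. With Q1 = 1 − 0.95 = 0.05 it gives 35.02, so 36. That slip is a separate matter, but it explains why 50 per arm has more than the planned 80% power before any relabelling.

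**Step 3: illustration of dilution.** Assume that a share r of true non-responders in each arm completes and is relabelled. Then p1 = 0.95 + 0.05r, p2 = 0.70 + 0.30r, and the difference is 0.25 × (1 − r). With n = 50 per arm, two-sided 5%, and p̄ the mean of p1 and p2:

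power = Φ{[(p1 − p2)√n − 1.96√(2p̄(1 − p̄))] / √(p1(1 − p1) + p2(1 − p2))}

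- r = 0: (0.25 × 7.071 − 1.96 × 0.537)/0.507 = 1.41, power 92%.
- r = 0.25: (0.1875 × 7.071 − 1.96 × 0.478)/0.459 = 0.85, power 80%.

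| r | p1 | p2 | Difference | Power |
|---|---|---|---|---|
| 0 | 0.950 | 0.700 | 0.250 | 92% |
| 0.15 | 0.958 | 0.745 | 0.213 | 86% |
| 0.25 | 0.963 | 0.775 | 0.188 | 80% |
| 0.41 | 0.971 | 0.823 | 0.148 | 68% |

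**Step 4: where r might lie.** The documents do not say. Three assumed cases, with Poisson counts in the last two, show how wide the range is:

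- Strict reading of the entry condition: r = 0.
- No drug effect, one 2-week titration look, and the trigger checked each fortnight against the halved level: labels conflict in 0 to 0.8% of children at 2 to 12, 20 and 30 seizures a month.
- Partial relapse: true monthly means of 0.4, 0.5 and 0.6 of baseline m at titration, at hold and taper, and in the final month, with a cap of 0.75m. Here r = P(completes, final count > m/2) / [1 − P(completes, final count ≤ m/2)]. This gives 0.15 to 0.41 at 3 to 12 a month and 0 at 2 a month.

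The last case was chosen to straddle the 50% cut-off. It shows what is possible, not what is expected.

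**The case against.** The strongest reply is that Study procedure is narrative about conduct. The Primary Objective and the dedicated Outcome evaluation section both give the 50% rule, and an analyst would naturally follow them. Study procedure also does not let every child who avoids the 1.5-times trigger go on. The child must have improved, and the final maintenance is described as one without a rise. Read strictly, these conditions make the two rules agree.

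Much of this stands, and it limits the point. It does not remove it: the completion sentence is a stated classification rule, improvement has no reference level, and no precedence is given. A child at 9 a month is better than at a baseline of 12.

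Three stronger readings are tempting but are not supported.

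- *A completer may end above baseline.* With a trigger set against baseline, 1.5 × 12 = 18 a month would not stop a child. If the reference were reset once between phases, the limit would be 0.50 × 1.5 × 1.5 = 1.125 of baseline. Either reading must set aside both the entry condition and the description of final maintenance.
- *The per-protocol comparison becomes 100% v 100%.* This would follow if responders were compared among completers under the completion label. Statistical Analysis item 3, however, attaches the per-protocol set to the absolute difference in increased seizure frequency, and no text says that responders will be compared in that set.
- *The trial loses much of its power.* The relabelled share is unknown and may be zero. At r = 0.25, power is still at the planned 80%.

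**Conclusion.** The concern holds as an inconsistency in the primary outcome definition. The completion sentence has no seizure threshold and can label as a responder a child whom Outcome evaluation (a) calls a non-responder. The 12, 6, 9 example shows this from the protocol's own rules, provided that the trigger refers to the post-titration level and improvement is judged against baseline. Under the strict reading there is no conflict.

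The size cannot be derived from the documents. The fall in the planned difference from 0.25 to 0.19, and in power from 92% to 80%, assumes that 25% of true non-responders are relabelled equally in both arms. It is an illustration, not an estimate. The sentence should be corrected because the rule is wrong as written and cheap to replace, not because a large loss has been shown.

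**What to change.** Replace the completion sentence in Study procedure with:

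*Responder status for the primary analysis is set only by Outcome evaluation (a): the monthly diary count in the final maintenance on the new combination (last 4 weeks, or the whole phase scaled to a month if shorter) is at most half the baseline monthly count. Completing all phases does not by itself make a child a responder. As an explicit part of that definition, children whose intervention is ended early count as non-responders.*

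Also state whether the earlier frequency in the stopping rule means the baseline or the post-titration level.

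**Cost.** No new data or visits are needed. The Diary Card section already provides a "self-reported diary card which is filled by the parents each day during the intervention phase", and the baseline monthly frequency is already recorded on the case report form. Titration, dose hold and taper stay as they are, and the stopping rule only gains a stated reference level. Figure 1 was not available to this review, so the length of the final maintenance is unknown here; the scaling clause covers a phase shorter than 4 weeks.

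**Downside.** The responder proportion may be somewhat lower in both arms, because completion alone no longer counts. A child stopped while still more than 50% below baseline will count as a non-responder; the new wording makes that an open choice.

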STUDY PROTOCOL

THE EFFICACY AND SAFETY OF FIRST LINE ANTI-EPILEPTIC DRUGS (AEDs) AS SUBSTITUTION THERAPY FOR CHILDREN WITH DRUG RESISTANT EPILEPSY

Protocol Number 22-09-1097

ABSTRACT

Background: Drug resistant epilepsy occurs around 30% of children with epilepsy. It is the failure to get seizure-free after combining two or more anti-epileptic drugs whether first- or second-line ones. Previous studies focus on the efficacy and safety between the two groups whether as add-on or substitution therapy mostly in newly diagnosed epilepsy children. However, the study that investigate first line Anti-epileptic Drugs (AEDs) as substitution therapy compared to second-line ones particularly among drug resistant epilepsy children is still lack. **Design**: It is an open-label, randomized controlled trial, which will be conducted in three referral hospitals in Jakarta, Cipto Mangunkusumo, Harapan Kita, and Fatmawati Hospital, from November 2022 until April 2023. The data will be collected from electronic medical record consisting of demographic, clinical characteristics, and brain CT scan or brain MRI, and diary cards that record daily drug consumption and adverse drug reaction. Self-administered QOLCE-55 questionnaire is used to assess the quality of life of the children. Furthermore, there will be EEG and laboratory examination prior and after intervention. The data will be recorded on Case Report Form that is filled by the researcher. Ethics committee approval is obtained from The Ethics Committee of The Faculty of Medicine, University of Indonesia-Cipto Mangunkusumo Hospital. Research permits would be issued by each institution where the study will take place.

Sample: There will be 100 participants, divided into 2 groups, the intervention and control. Fifty children in the intervention group will be treated with first line AEDs as the substitution therapy, while the other 50 participants in the control group will get second-line AEDs. The sample size is calculated based on the difference proportion of two independent groups.

Duration of the study: The study will take 14 weeks as a whole that consists of 6 phases including baseline, initial, titration, maintenance, tapering-of, stopping and another maintenance phase.

Introduction

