EEG recording results are categorized into:

- Normal: does not show of hypofunction/asymmetry/epileptiform waves
- Abnormal: shows a picture of hypofunction/asymmetry/epileptiform waves or a combination of 1 or more of these features

The subjects who show changes in their EEG are later grouped into groups of abnormal to normal or abnormalities that showed improvement. Abnormalities that show improvement, for example are hypofunction (slowing down) waves experience improvement or decreasing number of epileptiform waves.

Next, a proportion calculation is carried out in the form of the percentage to subjects who experience a change in the EEG and will be categorized into:

- Different : when a significant difference is shown in difference of proportion test of the group that reuses first line OAE line as substitution therapy and those that use standard therapy/
- Not different: when there is no significant difference is shown in difference of proportion test of the 2 groups.
- d. Difference in actual failure between the groups reusing first line OAE as substitution therapy and those taking standard therapy. Description of drug side effects in the form of frequency distribution and percentage of side effects in each group. Description of laboratory results in the form of frequency distribution and percentage of side effects in each group
- e. Factors contributing to decrease in seizure frequency (age, seizure onset, seizure type, family history of seizures, developmental delay, history of OAE, initial seizure frequency, initial EEG, structural brain abnormalities)

Sample size

The estimated sample size in this study was calculated using the different proportion formula for the 2 unpaired groups as follows ²⁹:

$$n1 = n2 = (\frac{Z_{\alpha}\sqrt{2PQ} + Z_{\beta}\sqrt{P1Q1 + P2Q2}}{P1 - P2})^{2}$$

Description:

n1 number of subjects who received the new drug (First Line OAE)

n2 number of subjects receiving standard drug (Second line OAE)

Alpha type one error (5%)

Zα alpha standard value 5% one-way hypothesis (1,96)

Beta type two error (20%)

Zβ beta default value 20% (0,84)

P2 proportion of decreased seizures on standard drugs (reference) for example 0.7

Q2
$$1-P2 = 1-0.7 = 0.3$$

P1-P2 difference in the proportion of reduced seizure that is considered significant between the new drug and the standard (defined by the researcher) for example 25% (0.25)

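### Adverse-reaction recording appears to stop when a child's intervention is ended, and side effects are reported as crude percentages, so the arms are not comparable if ending differs between them

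*Combined protocol and SAP*

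**What the plan says.** Study procedure: if seizures exceed one and a half times the previous frequency, the intervention is ended and the child goes back to the former combination. "The subjects are categorized as non-responder, and will be dropped-out". The text then lists resignation, non-compliance and unrelated death as the other grounds for drop-out, so ended children are grouped with children who leave the study. In the same section, children who complete every phase are the responders.

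Instrument of the study, Diary Card: adverse reactions come from a "self-reported diary card which is filled by the parents each day during the intervention phase". Under Follow-up data, the 2-weekly visits take their information from that diary, and the item recorded is reactions to the substitution therapy.

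Outcome evaluation, item d, plans a "Description of drug side effects in the form of frequency distribution and percentage of side effects in each group". Statistical Analysis item 5 plans summary tables of the same kind. Neither gives a safety population, a time window or an adjustment for exposure. The intention-to-treat and per-protocol rules stand under item 3, on drug effectiveness.

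Study Design says in general terms that the study closes once the last recruited patient has completed 14 weeks of follow-up. It does not say whether this covers children who have been dropped out.

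**The concern.** Read together, these sections make the length of safety observation depend on the efficacy outcome. A child who does badly on seizures leaves early, and nothing provides for recording reactions afterwards, including the period of the switch back. The trial is sized on the two arms differing in exactly that outcome.

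A crude percentage of children with a side effect rises with time at risk. If one arm loses more children early, its percentage covers fewer weeks, and the reader of the safety table cannot tell a safer drug from a shorter observation. Safety is in the title and the aim of the trial, and reactions that were never recorded cannot be recovered at analysis.

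**Working it through.** **Planning rates.** Sample size gives the control rate as "proportion of decreased seizures on standard drugs (reference) for example 0.7" and the first-line rate as 0.70 + 0.25 = 0.95. With z = 1.96 and 0.84, and Q1 as printed (0.5), the plan's formula gives

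[(1.96√(2×0.825×0.175) + 0.84√(0.95×0.5 + 0.7×0.3)) / 0.25]² = 48.91,

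close to the printed 49.56 and 50 per arm. But 1 − 0.95 is 0.05, not 0.5; with 0.05 the formula gives 35.02, or 36 per arm. That slip is a separate matter. It bears on this point only because the first-line non-response rate used below is 0.05.

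**Ratio of ending.** Planned non-response is 0.30 control and 0.05 first-line, so 0.30/0.05 = 6, or 15 against 2.5 children per 50. This is a ratio of ended interventions only if every non-responder is ended, as Study procedure implies. Outcome evaluation, item a, also counts as non-responders children whose seizures are unchanged or reduced by less than 50%, and they need not meet the ending threshold. If only a share of non-responders is ended (shares assumed):

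- 25% of control and 50% of first-line: 0.075/0.025 = 3
- 25% and 100%: 0.075/0.05 = 1.5
- 50% and 25%: 0.15/0.0125 = 12

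**Recorded time.** If all non-responders are ended at week w of the 12-week intervention (w assumed), mean recorded weeks are (1 − q)×12 + q×w, with q = 0.30 or 0.05. Control against first-line: 9.0 and 11.5 at w = 2; 10.2 and 11.7 at w = 6; 11.4 and 11.9 at w = 10. Control time is then 78%, 87% and 96% of first-line time.

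**Effect on the percentage.** Let both arms have the same 12-week risk R at constant hazard, and let recording stop at ending. The risk by week w is R_w = 1 − (1 − R)^(w/12), the observed percentage is (1 − q)R + q×R_w, and the gap between arms is (0.30 − 0.05)×(R − R_w). The documents give neither R nor w; both are assumptions.

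| R | w | Control | First-line | Gap (points, unrounded inputs) |
|---|---|---|---|---|
| 20% | 10 | 19.1% | 19.8% | 0.8 |
| 20% | 6 | 17.2% | 19.5% | 2.4 |
| 20% | 2 | 15.1% | 19.2% | 4.1 |
| 40% | 6 | 34.8% | 39.1% | 4.4 |
| 40% | 3 | 31.6% | 38.6% | 7.0 |

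A higher risk or earlier ending widens the gap.

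**Direction.** If all risk falls in the first 6 weeks and ending comes at week 6 or later, the gap is nil. If ended children carry a raised hazard, the gap shrinks and then reverses. With R = 20% in the others and w = 6, a doubled hazard gives 20.0% in both arms. A tripled hazard gives R_w = 1 − 0.8^1.5 = 28.5%, so control shows 0.7×20% + 0.3×28.5% = 22.5% against 20.4%.

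**The case against.** A reader might infer that the plan's own rates make ending six times as common in the control arm, and that the table will therefore make control look safer. The documents support neither step. The 0.70 and 0.95 are response rates, no rate of ending is given, and the protocol holds two definitions of non-responder that have not been reconciled. The reading also strains the plan's own allowance: 15 + 2.5 = 17.5 ended children per 100, before any other drop-out, against 10 added. If all 10 were ended children split 6:1 (8.6 and 1.4 per 50, or 17.1% and 2.9%), then at R = 40% and week 6 the percentages are 37.0% and 39.5%, a ratio of 1.07 rather than 39.1/34.8 = 1.13. These limits stand.

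Next, an ended child is off the substitution drug. Carry-over apart, the later weeks bring no new risk from it, so a lower percentage partly reflects real, shorter exposure. This also stands: a longer diary alone would not equalise the percentages.

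Third, that recording stops is an inference. Study Design mentions 14 weeks and monitoring of all recruited children, and the flow charts are not visible in the text available. That is right, but no section provides for recording after drop-out, so the text needs to say which is meant.

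Last, side effects are described, not tested. At 50 per arm, 34.8% against 39.1% carries a 95% interval of about ±19 points (1.96×√(0.348×0.652/50 + 0.391×0.609/50) = 0.19). The distortion is smaller than sampling error. It is still systematic, and nothing in the planned table would reveal it.

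**Conclusion.** The concern holds in a limited form. As written, reaction recording appears to end with the intervention, and the planned percentages take no account of time observed or on drug. If ending differs by arm, they are not comparable.

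The size rests on assumptions. If every planned non-responder were ended, with equal constant hazard and the risks and weeks tabulated, the control percentage would sit about 1 to 7 points below the first-line one. The factor of six is an upper figure on the Study procedure definition only; on the Outcome evaluation definition the ratio is unknown. The direction is uncertain, because it depends on the hoped-for superiority, on when reactions occur, and on the risk of ended children. A claim that the control arm will look safer goes further than the documents allow. Uncertain direction makes a crude percentage harder to read, so the plan should still be changed.

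**What to change.** - **Study procedure and Diary Card:** state that a child whose intervention is ended remains in safety follow-up, on the existing diary and 2-weekly visits, to the end of the same planned window as other children. Date each reaction and mark it as before or after ending. Reconcile this with the drop-out wording and with the 14-week statement in Study Design.
- **Outcome d and Statistical Analysis item 5:** use all treated children, by allocated arm, as the denominator. Report on-drug and post-ending reactions separately. Add reactions per child-week on the allocated substitution drug, with a 95% confidence interval for each arm.
- **Definitions:** reconcile the two definitions of non-responder, and report the number and timing of ended interventions by arm.

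The rate should sit beside the percentage, not replace it. If reactions come early, a rate can mislead the other way: equal counts over 10.2 and 11.7 weeks give a control rate 11.7/10.2 = 1.15 times the first-line one.

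The cost is protocol wording, one more line in the safety table, and some extra diary burden for the ended children's families: about 15 control and 2 to 3 first-line children if every planned non-responder were ended. The 2-weekly visits are already scheduled, and the protocol says hospital visits do not exceed usual care. No change to any dose or to the ending rule is proposed.
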